12.1.2 Pharmacokinetics

1) Serum AMG531 concentration

Serum AMG531 concentration will be summarized by descriptive statistics for each dose group at each sampling point. Time course of the serum concentrations of AMG531 will be presented in a chart.

2) Pharmacokinetic parameters

Pharmacokinetic parameters (including T_{max} , C_{max} , AUC_{0-t}) will be calculated for each subject and summarized by descriptive statistics for each dose group. Dose proportionality will be also assessed.

12.1.3 Safety

All AEs will be tabulated by MedDRA Preferred Terms (PTs) and System Organ Classes (SOCs) and number as well as percentage of subjects with each AE will be calculated by dose group. ADRs will be summarized in the same manner. All AEs will be graded with CTCAE ver.4.0 and number and percentage of subjects for each AE will be calculated.

All AEs occurred during the initial dose evaluation period will be separately summarized and analyzed as above.

Laboratory tests and vital signs will be summarized by descriptive statistics for all examination points of each dose group.

A listing of subjects with positive antibody against AMG531, TPO and TMP will be summarized by antibody expression.

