1 BACKGROUND AND STUDY RATIONALE

2 STUDY OBJECTIVES

The present study will be conducted to evaluate the efficacy and safety of AMG531 and to determine the recommended dose of AMG531 on the basis of its efficacy and safety when it is administered SC, QW at a dose of 1, 3, 6 or 10 µg/kg to the AA patients with immunosuppressive-therapy refractory thrombocytopenia and also to assess the pharmacokinetics of this product during the initial dose evaluation period. Its efficacy and safety during the extended period will also be evaluated. [REDACTED]

[figure not shown]
[REDACTED] - Efficacy and safety of AMG531 in the long term treatment beyond 1-year will be further evaluated for those showing continuous responses after 1 year treatment.

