3.4 Randomization

Subjects assessed to be eligible for the study will be randomized to either of the four dose groups (1, 3, 6, or 10 $\mu\text{g}/\text{kg}$) according to a static allocation procedure using the baseline platelet count (platelet $\leq 10 \times 10^9/\text{L}$ or $10 \times 10^9/\text{L} < \text{platelet} \leq 30 \times 10^9/\text{L}$). A written procedure for randomization will be created and the details will be specified in it.

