6.1.1 Initial-dose evaluation period (Week 1 to Week 8)

AMG531 will be administered at a dose of 1, 3, 6, or 10 µg/kg SC QW for 8 weeks. Dose adjustment (either escalation or reduction) will not be allowed during the initial dose evaluation period except for the cases defined in the 6.1.4 Criteria for discontinuing and resuming study treatment.

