6.1.2 Extension period (Week 9 to Week 52)

Initial dose of AMG531 for the extension period will be decided based on the efficacy and safety data observed during the initial dose evaluation period. If a subject does not show a platelet response at Week 9, the dose will be increased by one level according to Table 6.1.2-1 AMG531 dose adjustment (extension period) table. If no platelet measurement is available due to the platelet transfusion, then that week's platelet response is considered as having no response.

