9 ADVERSE EVENTS

9.1 Definition of adverse events

An adverse event (AE) is herein defined as any untoward medical occurrence in subjects received AMG531. An AE can therefore be any unfavorable or unintended sign (including an abnormal laboratory finding), symptom or disease, regardless of causal relationship to AMG531. An adverse drug reaction (ADR) is defined as any AE of which causal relationship to AMG531 cannot be ruled out (any events assessed to be other than “unlikely” or “not related”).

Laboratory results (hematology, serum chemistry, blood iron-related parameters, blood coagulation and fibrinolysis) will be evaluated for deviations (abnormalities) from normal range of each investigative site. In the event of an abnormal value (abnormal change), clinical significance of the abnormal change in comparison with baseline will be assessed. In consideration of pharmacological effects of AMG531, an increase in platelet, hemoglobin, reticulocyte, and/or neutrophil will be treated as abnormal only in the cases where the investigator considers it to be medically important.

For signs, symptoms, and abnormal laboratory findings associated with a disease (diagnosed disease), the disease will be treated as an AE. If any atypical sign is observed in that disease, the sign will be treated as an individual AE.

Observation period of both non-serious and serious adverse events will be the period between the start of study treatment through to the end of study visit or 4 weeks after the last administration of AMG531, whichever is longer. However, any event reported as delayed toxicity or the like attributed the investigational product will be treated as an adverse event as well.

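### Whole-study adverse event tables use the randomized starting dose, and no specified analysis shows safety by the dose received after Week 8, including 13, 16 and 20 µg/kg

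*Combined protocol and SAP*

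**What the plan says.** Section 12.1.3 plans that, for all AEs, "number as well as percentage of subjects with each AE will be calculated by dose group", with ADRs handled in the same way. It adds one restricted summary: "All AEs occurred during the initial dose evaluation period will be separately summarized and analyzed as above". For other safety data, "Laboratory tests and vital signs will be summarized by descriptive statistics for all examination points of each dose group".

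The term dose group is not defined in 12.1.3. The only definition is in section 3.4: "Subjects assessed to be eligible for the study will be randomized to either of the four dose groups", namely 1, 3, 6 and 10 µg/kg.

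The AE window in section 9.1 "will be the period between the start of study treatment through to the end of study visit or 4 weeks after the last administration", whichever is longer, so the whole-study tables can span the full treatment period to Week 156.

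The assigned dose is held only at first. Section 6.1.1 states "Dose adjustment (either escalation or reduction) will not be allowed during the initial dose evaluation period except for the cases defined in the 6.1.4". Section 6.1.2 then states "If a subject does not show a platelet response at Week 9, the dose will be increased by one level". Section 6.1.2.1 allows further single-level steps after 4 weeks at the previously escalated dose, at the investigator's discretion, to a ceiling of 20 µg/kg that does not depend on the starting group. The levels in Table 6.1.2-1 are 1, 3, 6, 10, 13, 16 and 20 µg/kg.

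The objectives (synopsis section II and section 2) include safety in the extension period and in treatment beyond one year.

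**The concern.** After Week 8 the group label no longer says what dose a subject is receiving. An AE that starts while a subject randomized to 1 µg/kg is on a much higher dose is counted under 1 µg/kg. The levels 13, 16 and 20 µg/kg can be reached only after Week 8, so they have no column in any specified safety table.

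If the whole-study table were read as a dose comparison, it would tend to flatten any relation between dose and toxicity, because all four groups can converge on the same upper levels. With 8 subjects per group, one subject moves a percentage by 1/8 = 12.5 points.

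Follow-up is also unequal. Section 11.1.1 withdraws subjects without a platelet response after 8 weeks at 20 µg/kg, and those who do not meet the long-term entry criteria. Others may continue to Week 156. A percentage of subjects with an event mixes these durations, and no exposure-adjusted rate is specified.

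**Working it through.** **Inputs**
- Group size: 8 per cohort, 32 in all (section 3.5.1). Check: 4 × 8 = 32. The plan gives no other figure to reproduce here; section 12.2 sets no significance level.
- Fixed-dose period: Weeks 1-8 (section 6.1.1).
- First step for a non-responder: Week 9, one level (section 6.1.2).
- Minimum interval for later steps: 4 weeks (section 6.1.2.1).
- Levels: 1, 3, 6, 10, 13, 16, 20 µg/kg (Table 6.1.2-1).
- Exit without response: after 8 weeks at 20 µg/kg (section 11.1.1, criterion 4).
- Data cut: when all subjects have completed Week 17 (section 12.1).

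**Formulas.** Let k be the number of levels from the starting dose up to 20 µg/kg (k = 6, 5, 4, 3 from 1, 3, 6, 10).
- First week at 20 µg/kg = 9 + 4(k − 1).
- Total weeks for a never-responder = 8 + 4(k − 1) + 8.
- Weeks at 13 µg/kg or more = 4 (at 13) + 4 (at 16) + 8 (at 20) = 16 from every starting dose.

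**Results on the fastest permitted path**

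| Starting dose (µg/kg) | First week at 20 µg/kg | Total weeks | Share at assigned dose | Share at 13 µg/kg or more |
|---|---|---|---|---|
| 1 | 29 | 36 | 8/36 = 22% | 16/36 = 44% |
| 3 | 25 | 32 | 8/32 = 25% | 16/32 = 50% |
| 6 | 21 | 28 | 8/28 = 29% | 16/28 = 57% |
| 10 | 17 | 24 | 8/24 = 33% | 16/24 = 67% |

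**Longest case.** A subject randomized to 1 µg/kg who first responds at 20 µg/kg and stays there to Week 156 has 8/156 = 5% of weeks at 1 µg/kg and up to (156 − 29 + 1)/156 = 128/156 = 82% at 20 µg/kg. All of it is counted under 1 µg/kg.

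**Week 17 cut.** Of the 16 weeks before the Week 17 visit, 8 (50%) already lie outside the fixed-dose period. On the fastest path, the dose held in Weeks 13-16 is 6, 10, 13 and 16 µg/kg from 1, 3, 6 and 10. Section 8.2.3 takes vital signs and hematology before dosing, so Week 17 values reflect those doses and not the next step up.

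**Follow-up.** A fastest-path never-responder contributes 24 to 36 weeks of treatment; a subject who completes contributes up to 156.

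**The case against.** The strongest reply is that dose selection is already covered. The aim in section 2 to "determine the recommended dose of AMG531 on the basis of its efficacy and safety" goes on to name the four starting doses, and the synopsis speaks of the initial dose. The Week 1-8 summary serves that aim, in a period when doses are fixed apart from changes under section 6.1.4. This stands: a reader might infer that the dose-finding comparison is compromised, and the documents do not support that.

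Second, the plan is descriptive and never calls the whole-study table a dose-toxicity comparison. For a starting dose followed by titration, AEs by starting group are a legitimate summary of each strategy. This also stands, and is the reason to keep the table and label it.

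Third, section 12.1.4 allows further exploratory analyses and section 12.5 promises a detailed analysis plan, which is not among the documents. It would therefore be too strong to say that safety at 13, 16 or 20 µg/kg can never be shown. But neither section commits to such an analysis.

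Fourth, only the Week 9 step is required; later steps are discretionary, so the ladder is the fastest path. It would also be wrong to take the assigned-dose share of a never-responder as 8/52 = 15%, since the fastest-path never-responder from 1 µg/kg leaves after 36 weeks (8/36 = 22%). Nor do the documents show that most subjects will reach the upper levels.

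Finally, a table by dose at onset has sparse cells and is confounded with non-response and time on study. That limits its use but does not remove the gap.

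**Conclusion.** The point holds as a gap in the specified safety reporting after Week 8. The whole-study AE and ADR tables describe starting-dose strategies, and no analysis specified in the document shows safety by dose received in the extension and long-term periods, or at 13, 16 or 20 µg/kg at all. Those periods are stated safety objectives.

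On the fastest path, a never-responder has 22%, 25%, 29% and 33% of treatment at the assigned dose and 44%, 50%, 57% and 67% at 13 µg/kg or more, from 1, 3, 6 and 10 µg/kg respectively. These figures assume a step at every 4-week opportunity, no interruption or reduction, and exit after 8 weeks at 20 µg/kg. Slower escalation changes the shares, and a subject who stays below 13 µg/kg has none there.

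The conclusion also rests on reading dose group as randomized group, which is the natural reading of section 3.4 but is not stated in 12.1.3. The primary endpoint and the Week 1-8 comparison of starting doses are not affected, and no view is taken on the dosing rules.

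**What to change.** In section 12.1.3:

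1. Define dose group as the randomized group, and use the Week 1-8 table as the between-dose safety comparison.
2. Keep the whole-study table by group, but label it a starting-dose strategy summary.
3. Add a descriptive table of AEs and ADRs by dose level at onset, taken as the last dose given before onset, with subject-weeks at each level as denominator. Include an off-drug category for subjects who have discontinued after tapering (section 6.1.3.3) or whose dosing is interrupted (section 6.1.4), and state when a subject moves into it. Without it, events after tapering to discontinuation would fall under 3 µg/kg.

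The cost is one extra table. AE onset dates are collected (section 9.2), and the plan's own rules on doses received (sections 11.1.1 and 12.6.2) already need dosing records. Design and treatment do not change.

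The table has limits that should be printed with it. With 32 subjects over seven levels the cells will be sparse. Dose at onset is confounded with non-response and time on study. It also suits delayed or cumulative events poorly, so marrow fibrosis, cytogenetic change and AML/MDS should be reported separately; section 8.2.7 already collects them.

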12.1.4 Additional analyses

Additional exploratory analyses of the data will be performed as deemed to be appropriate.

12.2 Level of significance

Level of significance is not specified, since no statistical assumptions are provided in this study.

12.3 Stopping rules for the study

No stopping rules based on statistical evidence are specified.

12.4 Handling of missing, unused, and abnormal data

Any missing data on platelet, hemoglobin, and neutrophil for evaluating efficacy response will be handled as a missing value and will not be imputed with an alternative value using a statistical approach.

If data from a particular subject needs to be examined how to handle them because of an event unexpected at the start of the study, how to treat such data will be decided before database lock.

12.5 Development of the statistical analysis plan and procedure for reporting deviations from the original statistical analysis plan

The detailed statistical analysis plan including the analyses described in this section will be finalized before database lock. Any major change to the statistical analysis plan will be described in the clinical study report.

12.6 Analysis Subsets

The analysis sets are defined below. For efficacy analysis, PPS and FAS will be used, with PPS as the primary analysis set.

Whether or not to include each subject in a particular set will be determined before database lock.

12.6.1 Full Analysis Set (FAS)

Efficacy will be assessed in the subjects of FAS who meet all of the following criteria:

- Subjects received at least one dose of AMG531; and
- Subjects whose platelet count is measured before and at least one point after dosing AMG531.

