12.1.1.1 Primary endpoint

The primary endpoints will be evaluated based on the Per Protocol Set (PPS). The proportion of subjects achieving a platelet response at Week 9, and two-sided 95% confidence interval will be calculated. Platelet response is defined as 1) achieving absolute platelet increase of $\geq 20 \times 10^9/L$ above baseline or 2) increase to $\geq 10 \times 10^9/L$ and by at least 100% from baseline.

Robustness of the results will be evaluated by the analysis calculated in the same manner based on the full analysis set (FAS).

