12.6.2 Per Protocol Set (PPS)

Efficacy will be assessed in the population of PPS comprised of subjects of FAS who meet all the following criteria. PPS is the primary efficacy analysis set.

- Subjects who meet all of the inclusion criteria and none of the exclusion criteria;
- Subjects who have received ≥ 6 times of the specified dose (dose interruption according to the dose discontinuation criteria (section 6.1.3) will be considered as

being dosed but dose interruption due to SAE will not be considered as being dosed) in the initial dose evaluation period; and

- Subjects with no major violations of the study protocol in the initial dose evaluation period.

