12.6.4 Safety analysis set

Safety will be assessed in the subjects of safety analysis set who meet the following criterion:

- Subjects received at least one dose of AMG531.

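### The FAS requires a platelet count after dosing, so a dosed subject lost before any count drops out of the only prespecified robustness check instead of counting as a non-responder

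*Combined protocol and SAP*

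**What the plan says.** All references are to the combined protocol and SAP.

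- **FAS (12.6.1).** There are two conditions. The first is at least one dose. The second is "Subjects whose platelet count is measured before and at least one point after dosing AMG531".
- **PPS (12.6.2).** It is drawn from the FAS: "Efficacy will be assessed in the population of PPS comprised of subjects of FAS who meet all the following criteria". One of those criteria is "Subjects who have received ≥ 6 times of the specified dose" in the initial dose evaluation period.
- **Use of the sets (12.6).** "For efficacy analysis, PPS and FAS will be used, with PPS as the primary analysis set". Sections 12.1.1.1 and 12.1.1.2 name a repeat of the same calculation in the FAS as the robustness check for the primary and secondary endpoints. No other check is prespecified.
- **Safety set (12.6.4).** The only condition is "Subjects received at least one dose of AMG531".
- **Missing data (12.4).** "Any missing data on platelet, hemoglobin, and neutrophil for evaluating efficacy response will be handled as a missing value", with no imputation. The one rule that turns an absent count into no response is in the dosing text (6.1.2), and it covers only counts that are unavailable because of a platelet transfusion.

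**The concern.** An FAS repeat is useful next to a per-protocol primary analysis because it brings back the subjects whom the per-protocol rules remove. Here the second FAS condition depends on something that happens after treatment starts. A dosed subject who dies or is lost before any post-dose platelet count is in the safety set but in neither efficacy set. No section scores that subject as a non-responder.

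The check is then weakest for the earliest losses, and its error has one direction. Compared with counting non-response, leaving such a subject out can raise the proportion or leave it unchanged, but cannot lower it. With 8 subjects per dose group, one subject is visible in the result. The groups will be read side by side, because the study aims to recommend an initial dose.

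The condition also governs FAS proportions that do not rest on a post-dose platelet count, such as platelet transfusion independence.

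**Working it through.** **Inputs.** Eight subjects per dose group in four groups (3.5.1). The primary estimate is the Week 9 response proportion with a two-sided 95% confidence interval (12.1.1.1). The interval method is not named, so exact Clopper-Pearson intervals are assumed. The plan gives no response rate, loss rate, power or significance level (12.2 says none is specified).

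**The plan's own figure.** 4 × 8 = 32, which agrees with the stated total. Nothing else about the sample size can be derived.

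**Which analysis the condition changes.**

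| Dosed subject with no post-dose count | In the set? | Rule that decides it |
|---|---|---|
| Safety set | yes | one dose is enough (12.6.4) |
| FAS | no | post-dose count required (12.6.1) |
| PPS | no | not in the FAS, and also short of six doses (12.6.2) |

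Section 12.6.2 lets a dose interrupted under the discontinuation criteria count as given. Such an interruption is triggered by a high platelet count, so it cannot help a subject who has no count. Deleting the FAS condition would therefore leave the PPS as it is and change only the FAS repeat.

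**When the condition is triggered.** The first scheduled post-dose count is the Week 2 pre-dose sample: Day 8, with ±3 days allowed (8.2.2). A subject who stops after one dose is due hematology one week after that dose (8.2.5) and again at four weeks (8.2.6). If a safety withdrawal makes those visits impossible, the procedures are to be done as soon as termination is decided (11.1.2). The subject leaves the FAS only if all of these are missed. Section 12.1.1 bars counts taken outside scheduled visits from efficacy assessment, but the plan does not say whether such a count would qualify a subject for the FAS.

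**Size in one dose group.** Suppose x of 8 respond and one non-responder has no post-dose count.

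Counted as a non-responder: x/8. Left out: x/7. Gap: x/7 − x/8 = x/56.

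| x | Counted, x/8 (95% CI) | Left out, x/7 (95% CI) | Gap, points |
|---|---|---|---|
| 1 | 12.5% (0.3 to 52.7) | 14.3% (0.4 to 57.9) | 1.8 |
| 4 | 50.0% (15.7 to 84.3) | 57.1% (18.4 to 90.1) | 7.1 |
| 6 | 75.0% (34.9 to 96.8) | 85.7% (42.1 to 99.6) | 10.7 |
| 7 | 87.5% (47.3 to 99.7) | 100.0% (59.0 to 100.0) | 12.5 |

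With x = 0 both proportions are 0%. With two such losses in one group and x = 4, the figures are 4/6 = 66.7% against 4/8 = 50.0%.

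**Size over all groups.** With 16 responders, 16/31 = 51.6% against 16/32 = 50.0%, a gap of 1.6 points.

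**Would deleting the condition be enough?** No. Section 12.4 leaves absent counts missing. Section 12.1 expresses percentages relative to the total number of subjects, which only implies a denominator and does not score anyone. A subject with a Week 2 count who is lost in Week 3 is already in the FAS, and that subject's Week 9 status is just as undefined. A rule limited to subjects with no post-dose count would make a first-week loss a failure and leave a Week 3 loss open.

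**The case against.** The strongest reply is that this is a narrow condition on a supportive set. Much of that stands.

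- **Primary result.** A reader might infer that the FAS wording biases the primary analysis. It does not. The PPS loses the same subjects through its six-dose minimum.
- **Early death or loss.** A reader might infer that every first-week death or dropout leaves the FAS. The trigger is having no post-dose count at all, and the visits in 8.2.5, 8.2.6 and 11.1.2 should supply one for most subjects who stop early.
- **Frequency.** A reader might try to show that the event is likely. With a per-subject probability p, the chance of at least one case among 32 is 1 − (1 − p)^32, or 27.5%, 47.6% and 80.6% for assumed values of 1%, 2% and 5%. Nothing in the documents supports any of these values, so no conclusion is drawn from them.
- **Known failures.** A reader might call the omitted subjects certain failures. That holds for a death before Week 9. The Week 9 status of a subject lost to follow-up is unknown, and scoring it as non-response is a convention, though the usual and cautious one.
- **Other endpoints.** The bleeding scale is taken at Week 1 and not again until Week 9 or end of treatment. A subject with no follow-up has no change to summarise, so a wider FAS adds nothing there.
- **Dose comparison.** No test between doses is planned, and at 8 per group the intervals are wide either way.

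Sections 12.4 and 12.1.4 also leave room for case-by-case decisions before database lock and for exploratory analyses. Neither states a rule, and in an open-label study such decisions may be made with the dose known. What remains is a one-directional weakness in the only prespecified check, which wording alone can remove.

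**Conclusion.** The point holds as a limited, inexpensive improvement. A dosed subject without a post-dose platelet count is left out of the FAS repeat, and no section counts that subject as a non-responder. Relative to counting non-response, the FAS proportion in the affected group is x/56 higher for one such loss among 8. That is 1.8 to 12.5 points for 1 to 7 responders, and nothing when there are none.

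These sizes assume one loss in a group of 8 and that all 7 remaining subjects are in the denominator. The intervals assume the exact method. How often the event would occur cannot be estimated from the documents, and the scheduled follow-up suggests that it would be rare. The primary PPS estimate is not affected.

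**What to change.** 1. In 12.6.1, remove the requirement for a post-dose platelet count, so that the FAS is all randomised subjects who received at least one dose.
2. In 12.4 and 12.1.1, add a rule for the FAS analyses of the response proportions. For example: *a FAS subject without a usable platelet count at Week 9 remains in the denominator and is counted as a non-responder, whatever the time of loss; for endpoints assessed at any time in a window, the same applies to a subject with no qualifying count in that window.*
3. Apply the same rule to the platelet transfusion-independence proportion. A subject whose follow-up is too short to show eight consecutive transfusion-free weeks counts as not independent.

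Item 2 is needed as well as item 1. Without it, 12.4 would leave the added subjects missing, and losses between Week 2 and Week 9 would stay undefined.

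The cost is a wording change in three sections, with no new data or visits. The FAS proportions may come out slightly less favourable.
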